## Protocol Body

### 1.0 Objectives

Primary Objectives:

[figure not shown]
1) To determine whether oral ribavirin given for therapy of Respiratory Syncytial Virus (RSV) upper respiratory tract infection (URI) can prevent its progression to Lower respiratory tract Infection (LRI)-pneumonia, when compared to aerosolized ribavirin – modified regimen in HSCT recipients at moderate or high risk for progression.

Secondary Objectives:

- 1) To determine the safety of oral ribavirin therapy when compared to aerosolized ribavirin.
- 2) To calculate the cost effectiveness of using oral ribavirin when compared to aerosolized ribavirin.
- 3) To compare RSV viral loads in nasal washes and/or other respiratory specimens and RSV neutralizing antibodies in serum between patients on both arms of the study and a observational arm where low risk patients for progression are not receiving either regimen of ribavirin.

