## **6.0 Pretreatment evaluation**

6.1 Patients will be identified based on eligibility criteria. After a patient is identified and expresses interest, the study will be explained by the study team and the informed consent form will be given to the patient to be signed.

6.2 All patients should have an initial nasopharyngeal wash positive for RSV by rapid testing and/or culture at onset of therapy unless a positive result was obtained from a specimen during the preceding 72 hours.

6.3 Routine blood tests will be obtained as per the standard of care within 48 hours of study entry as follows:

A. Hemoglobin, Hematocrit, WBC with differential if available, platelets count, pregnancy test from urine or blood for women of child-bearing potential.

B. Chemistry profile – BUN, Creatinine, Total bilirubin, Aspartate Aminotransferase (AST) and/or Alanine Aminotransferase (ALT), and alkaline phosphatase.

C. Nasal washes and blood at the time of enrollment will be taken and saved for testing for RSV viral loads and titers and neutralizing antibodies in serum at a later date (see section 7.1).

6.4 An initial history and physical examination.

6.5 A chest radiographic study (i.e. chest radiographs and/or CT scan of chest) will be obtained if not done within preceding 48 hours as per standard of care.

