## **7.0 Evaluation During Study**

7.1 Nasal washes for the therapeutic arm will be repeated on day 3  $\pm$  1 day, day 7 ( $\pm$  1 days), day 14 ( $\pm$  1 days), and by day 14  $\pm$  1 days after end of therapy; and will be stored at 6-8 degrees Celsius until it can be taken to [name] laboratory for analysis. Blood specimens for the therapeutic arm will be drawn at enrollment and 14  $\pm$  1 days after end of therapy. These specimens will be shipped for batch analysis to [name] laboratory at Baylor College of Medicine ([name]) for viral loads, titers and for neutralizing antibodies testing (Please see references 7-9 for methods). For patients on the observational arm, nasal washes for RSV viral loads will be done once a week for 4 weeks and blood specimens will be taken at enrollment and the 4th week on study for neutralizing antibodies testing and for RSV viral load. Leftover of blood and nasal washes will be saved at [name] laboratory for future testing.

7.2 Routine blood tests as in 6.3 will be repeated at least once weekly until study is completed as part of the standard of care for patients who are on the therapeutic arms. Patients on observational arm will have routine blood tests done at enrollment and the 4th week on study.

7.3 Patients will be monitored for signs and symptoms of URI and LRI (Please see Appendix G and H for Clinical Assessment Tool). Patients who are hospitalized will be seen 2 times a week from the time of enrollment until discontinuation of ribavirin therapy. Patients who are not hospitalized will be monitored twice a week until the discontinuation of therapy or once a week for 4 weeks for patients on the observational arm. Any possible evidence of pulmonary infection should be confirmed by a repeat chest radiographic study and/or oxygen saturation level. All patients on the therapeutic arms will have a final visit 14 days  $\pm$  1 days after end of therapy.

7.4 Follow-up after end of therapy or discontinuation of therapy: Patients will be seen 14 days  $\pm$  1 days after discontinuation of therapy for the final determination of response, unless there is progression to pneumonia. In the latter scenario or if study drug is discontinued for Serious Adverse Events (SAEs), patients will be followed for up to 14 days from the time of occurrence of the event or until resolution of the SAE whichever occurs last or up to 30 days from the last dose of the study drug.

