### *Analysis*

We will use descriptive statistics to summarize the demographic and clinical characteristics of patients in each treatment arm and the observational arm.

We will use the Cochran-Mantel-Haenszel test stratified by risk group to test the null hypothesis stated above. We will also estimate the treatment failure rates with exact 95% binomial confidence intervals for each treatment arm.

We will tabulate adverse events for each treatment arm by severity and relationship to study therapy.

We will use descriptive statistics to summarize the costs associated with each treatment arm. Costs for each patient will be calculated as described in section 10.0 above.

We will use descriptive statistics to summarize the RSV viral loads and neutralizing antibodies for each treatment arm and the observational arm.

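### Objective 3 is comparative, but Section 11.0 plans only descriptive summaries of viral load and antibodies; a baseline-adjusted difference between the randomised arms needs no new samples

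*Combined protocol and SAP*

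**What the plan says.** Section 1.0 gives the third secondary objective as "To compare RSV viral loads in nasal washes and/or other respiratory specimens and RSV neutralizing antibodies in serum", across the two randomised arms and the untreated low-risk observational arm.

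The matching analysis is one sentence in Section 11.0, Analysis: "We will use descriptive statistics to summarize the RSV viral loads and neutralizing antibodies for each treatment arm and the observational arm".

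The sampling plan supports more than that:

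- **Enrolment, all patients** (Section 6.3 C): "Nasal washes and blood at the time of enrollment will be taken and saved for testing for RSV viral loads and titers".
- **Washes, randomised arms** (Section 7.1): "Nasal washes for the therapeutic arm will be repeated on day 3", then on days 7 and 14, and finally 14 days after therapy ends. Each visit has a one-day window.
- **Washes, observational arm** (Section 7.1): "nasal washes for RSV viral loads will be done once a week for 4 weeks". No windows are given.
- **Blood, randomised arms** (Section 7.1): "Blood specimens for the therapeutic arm will be drawn at enrollment" and once more, 14 days after therapy ends.
- **Blood, observational arm** (Section 7.1): enrolment and week 4.

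Section 3.0 describes 5 to 10 days of therapy. Section 5.0 recommends up to 10 days and lets the treating physician extend it. Randomisation is stratified by moderate versus high risk (Section 11.0, Randomization).

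**The concern.** A table of summaries by arm lets a reader look at the arms side by side. It does not give a difference or say how precisely that difference is known. Section 11.0 also leaves open the day of comparison, the scale, the role of the enrolment value and the handling of results below detection. Each of these could be settled after the data are seen.

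Two things are at stake. The first is precision: an enrolment load is measured in every patient, and the analysis text assigns it no role. The second is timing: the final wash and the only post-baseline blood are tied to the end of therapy in the randomised arms but to the calendar in the observational arm. A comparison at the final sample would mix time since infection with treatment and risk group.

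The virology matters here because the trial is open label and the primary endpoint will be sparse. At the planned rates about 38 × (0.20 + 0.15) = 13.3 failures are expected, tested at a one-sided level of 0.20. A laboratory measure is useful supporting evidence beside that.

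**Working it through.** **1. The plan's own figure.** Section 11.0 gives no sample size or precision for objective 3. The 38 per arm is for the primary endpoint. From the stated inputs (failure rates 0.20 and 0.15, margin 0.10, one-sided 0.20, power 80%), the distance to the margin is 0.10 − (0.15 − 0.20) = 0.15. The fixed-design size is

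n = (0.20×0.80 + 0.15×0.85) × (0.8416 + 0.8416)² / 0.15² = 0.2875 × 2.833 / 0.0225 = 36.2, so 37 per arm.

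With the stated futility look at half the information (nominal levels 0.6040 and 0.2116, z = −0.264 and 0.801), 38 per arm gives 80.3% power and an overall one-sided level of 0.200. The design reproduces, and nothing below changes it.

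**2. Timing of the final sample.** In the randomised arms this is therapy duration + 14 days, counting from the start of therapy. In the observational arm it is about day 28.

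| Days of therapy | Final sample, randomised arms | Gap to day 28 |
|---|---|---|
| 5 | day 19 | 9 days |
| 7 | day 21 | 7 days |
| 10 | day 24 | 4 days |
| 14 | day 28 | 0 days |

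These are before visit windows and before the difference in clock. Section 5.0 counts observational follow-up from diagnosis, and Section 4.0 lets the positive specimen be up to 72 hours old. The two randomised arms follow one rule, so their final samples separate only if therapy durations differ.

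**3. Which days are shared.** Days 7 and 14 are fixed for both randomised arms. In the observational arm they follow approximately from weekly washes. This helps viral load only: each patient has a single post-baseline blood sample, so antibodies have no common day to move to.

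**4. What adjustment for enrolment load is worth.** The documents give no SD and no correlation r between enrolment and follow-up load. Both are assumed here, with 38 per arm, complete samples and no censoring.

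- Variance factor: 1 − r²
- Equivalent unadjusted size: 38 / (1 − r²)
- 95% half-width: 1.96 × SD × √(2(1 − r²)/38)
- Detectable difference (80% power, two-sided 0.05): (1.96 + 0.8416) × SD × √(2(1 − r²)/38), with SD = 2 log10

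| r | Variance factor | Equivalent n per arm | Half-width (SD units) | Detectable difference (log10) |
|---|---|---|---|---|
| 0 (unadjusted) | 1.00 | 38 | 0.45 | 1.29 |
| 0.3 | 0.91 | 42 | 0.43 | 1.23 |
| 0.5 | 0.75 | 51 | 0.39 | 1.11 |
| 0.7 | 0.51 | 75 | 0.32 | 0.92 |

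**5. Where adjustment does not help.** The observational arm has immunodeficiency scores of 0 to 2 and the randomised arms 3 or more. With no overlap, no covariate makes that contrast causal. For antibodies, sampling day in the randomised arms is therapy duration + 14. Duration is decided after randomisation, so adjusting for sampling day could bias the randomised contrast.

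**The case against.** The strongest reply is that this is a secondary objective of a phase II screening trial. Costs and adverse events are also handled descriptively, so restraint about unpowered inference may be deliberate. Side-by-side summaries of randomised arms are a form of comparison. That much stands, and it limits the weight of the point. It does not explain why an estimate with an interval should be left out when the data are already collected; an interval is not a claim of power.

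Several stronger readings are tempting and are not supported:

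- **That the plan compares arms at the final sample.** Section 11.0 names no time point, and a summary by visit is at least as natural. The timing gap is a risk that the wording leaves open.
- **That the enrolment load is discarded.** It is collected, and nothing excludes it from the summaries. The text simply gives it no role.
- **That objective 3 cannot be answered.** It can be answered informally.
- **That viral load is the only quantitative antiviral measure.** Sections 6.3 and 7.1 also list titers.
- **That extended therapy widens the gap to week 4.** Extension from 10 to 14 days closes it. Stopping before 5 days would widen it.
- **That the 2 log10 fall cited in Section 2.0 scales the detectable difference.** That is a within-patient fall in an uncontrolled series. The contrast here is between two arms that both receive ribavirin.

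Two further cautions also stand. Up to two aerosolized doses are allowed before enrolment (Section 4.0), so the enrolment load is not always pre-treatment. Follow-up and therapy may also change after progression (Sections 7.4 and 9.1).

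**Conclusion.** The point holds as a free improvement to a secondary objective. The objective is to compare; the analysis only describes, and it states no between-arm estimate, analysis day or use of the enrolment value. Adjusting for enrolment load would reduce the variance of the randomised contrast by 9%, 25% or 49% at r = 0.3, 0.5 or 0.7. Those figures assume complete, uncensored samples, so missed washes or many undetectable results would reduce the gain. The timing gap of about 4 to 9 days applies to any summary at the final sample against the observational arm, for 10 down to 5 days of therapy. It can be avoided for viral load, but for antibodies it can only be reported. The primary test and the 38 per arm are unaffected.

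**What to change.** In Section 11.0, Analysis, replace the single sentence with the following:

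- **Viral load, randomised arms.** Estimate the oral-minus-aerosolized difference in log10 viral load at days 7 and 14 with a 95% confidence interval, by ANCOVA or a repeated-measures model with enrolment log10 load and risk group as covariates. Treat values below detection as censored. Keep every randomised patient in the assigned arm, including those who progress, and state how washes missed after progression are handled. State the day from which visits are counted, and confirm that the enrolment wash is taken before allocation.
- **Antibodies, randomised arms.** Report the difference in log fold-rise from enrolment with a 95% confidence interval, adjusted for enrolment titre and risk group. Report the actual sampling day by arm alongside it, and do not adjust for that day.
- **Observational arm.** Keep it descriptive. Show viral load by scheduled week, beside the randomised arms at about days 7 and 14, and show the week-4 antibody result with the timing difference noted.

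If the sponsor wants description only, objective 3 should be reworded to say so. The cost is a paragraph of text and a modest amount of analysis, with no new samples or visits and no change to the sample size.

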## **12.0 Reporting Requirements & Drug Accountability**

A case report form will be required for each patient entered on study (please see appendix G and H). An interim safety analysis of the data focusing on SAEs will be done after each winter season.

We will maintain the study drug records of aerosolized ribavirin including documentation of the amount received and duration as per respiratory therapy protocol. For oral ribavirin, subjects should bring their medication bottles back at each visit even if they are empty so site personnel can assess study drug compliance.

